OFFICIAL TITLE:
Regulation of Cervical Mucus Secretion

PRINCIPAL INVESTIGATOR:
[name], MPH

Assistant Professor, Department of Obstetrics and Gynecology
Oregon Health & Science University

NCT No:
NCT02969590

Protocol Version Date:
November 12, 2018

Project Summary

Hormonal contraception remains the primary form of contraception used by US women. These methods include oral contraceptive pills, rings, patches, injectables, implants and the progestin containing intrauterine device (IUD). All of these progestin-based hormonal methods are thought to cause thickening of the cervical mucus that causes poor sperm penetration. While it is widely accepted that progesterone is a mediator of mucus changes observed at midcycle, the regulation of this effect is not well understood. Subsequently, lingering questions regarding the onset and extent of progestins actions on cervical mucus affects our prescribing practice of current progestin-based contraception. Moreover, our neglect of cervical mucus over the last 40 years has perhaps led us to overlook a biologically intuitive target for non-hormonal contraceptive development.

Most of our current knowledge of cervical mucus remains based in clinical studies done in the 60s and 70s with the advent of various forms of progestin only contraception such as the mini-pill. However, these studies suffer from serious limitations. First, mucus changes progressively under the influence of increasing amounts of estrogen by becoming less viscous and more favorable to sperm penetration. Mucus evaluation of a progestin must be timed to coincide with the peak effect of endogenous estradiol and potential trough effect of the contraceptive steroid, a complex problem for many study designs. Additionally, ovulation presents an important confounder that is not accounted for in many of the mini-pill studies when ovulation occurred 15-70% of the time. With ovulation there is also endogenous progesterone being produced, subsequently suppressing endogenous estradiol production. As there is a convolution of forces on mucus from both estradiol withdrawal and endogenous progesterone, the early and late effects of progesterone signaling remain incompletely understood.

We propose studies to evaluate the temporal changes in human cervical mucus in response to progesterone and progestins as an initial step toward clarifying these relationships. Our hypothesis is that direct effects of progesterone on the endocervix, independent of estrogen withdrawal, cause contraceptive changes to cervical mucus. To study this, we plan to conduct a randomized, prospective, crossover study examining cervical mucus changes in a small cohort of women in whom we will suppress circulating hormonal levels by administering a GnRH agonist. We will then artificially replace Estrogen and Progesterone in order to differentiate their effects on clinical and laboratory measurements of mucus quality. We will be looking closely at the immediate changes in mucus when .35 mg of norethindrone, a marketed drug is administered in this experimental setting. We will also collect cervical cell samples at various time points and perform RT-PCR to determine whether genes for membrane bound progesterone receptor are expressed and regulated by Estrogen and Progesterone.

We believe this research will offer important, immediate insight into progestin regulation of cervical mucus. However, we also expect this to lay important foundations for future studies both clinical and laboratory based. We hope our model will provide the vigorous conditions with which we can evaluate mucus effects from other progestin-based contraceptives such as the levonorgestrel-releasing intrauterine system or the etonorgestrel implant. Last, elucidation of the relationship between membrane bound progesterone receptors and cervical mucus will offer new biochemical pathways to target for contraceptive development.

1. DESCRIPTION OF THE PROJECT

1.1 Rationale and objectives of the study

1.1.1 Rationale

At this time, the majority of women in the United States using contraception rely on short acting, reversible, hormonally-based contraceptive methods. More than a quarter rely on combined oral contraceptive pills; this increases to 35% when other hormonal methods that inhibit ovulation (injectables, rings, patches and implants) are included[1]. Although there are many peripheral benefits to the use of hormonal contraception, for many women the perceived risks of hormonally based contraception outweigh perceived benefits[2][3][4]. A smaller, but no less important group of women have relative (e.g. obesity) or absolute contraindications to hormonal contraception due to thrombosis risk associated with estrogen [5]. It is widely believed that estrogen-free hormonal methods that do not block ovulation (e.g. norethindrone progestin-only pill; LNG-IUS) work at least in part by inhibiting cervical mucus [6–9]. Although these methods exploit the progesterone-mediated changes in cervical mucus, we know little about how progesterone regulates this effect. We have the potential for developing an easy to use, non-hormonal contraceptive based on mucus thickening alone with a better understanding of the regulation and modification of this secretory machinery.

Cervical mucus is thought to rely on a careful balance of its solid (primarily mucin proteins) and liquid components to give it the qualities that make it either facilitate sperm transport into the uterus or help it serve as a barrier to sperm and other pathogens. Mucus production occurs in the endocervix where a single layer of columnar cells line the endocervical canal, producing a mixture of water, ions, lipids, mucin proteins and non-mucin proteins. Mucin proteins are large glycoproteins, with highly anionic carbohydrate ends that bind liquid and form polymer networks which either trap microorganisms (including sperm) or facilitate sperm transport depending on their orientation [10–12]. Despite forming the critical backbone to the gel-like quality of mucus, mucins comprise only 2-5% of the mucus content by weight while water content ranges from 90% when mucus is pre- or post-ovulatory, and up to 98% at midcycle[13][11]. It appears that a number of ion channels are involved in regulation of fluid content in mucus secretion including sodium channels, calcium-based chloride channels, aquaporins and the cystic fibrosis transmembrane conductance regulator (CFTR)[10,14].

The production of mucin protein genes and the flow of water and channel ions has been shown to be directly correlated to estrogen and progesterone levels[12,14,15]. However, to date, no direct mechanistic pathway exists describing the steroid regulation of mucus production. We know estrogen promotes mucin gene transcription and protein levels as well as fluid transudation and ion exchange[15,16]. Meanwhile, these effects are all muted with the presence of progesterone in the luteal cycle. Experiments using both anti-estrogens and synthetic progestins demonstrate that these compounds affect mucus quality and sperm penetrability [17–20]. However, it remains unclear what changes to cervical mucus result from inhibition or withdrawal of estrogen-based effects and what changes derive from direct progesterone actions on endocervical cells. Previous experiments of progesterone-based contraceptives were done in normal cycling women where drug treatment occurs in the setting of endogenous hormone production.

Steroid regulation of mucus likely affects multiple components of the cellular machinery at various time points in the synthesis and secretion of cervical mucus. Some experiments monitoring mucus changes following ovulation (or exogenous administration of progestin) demonstrate changes in quantity and quality much faster than what would be expected from the

classical mechanisms through which steroids are thought to work. In the well-characterized, classic nucleus-based paradigm, progesterone and estrogen bind to receptors located in the cytosol, but must be transported into the nucleus where they bind to the hormone response element (HRE) located within specific gene promoter regions and activate transcription [21]. This is generally a “slow” process (e.g. several hours to days) as it relies on DNA transcription and RNA translation to produce proteins that promote cellular changes. However, there is evidence suggesting changes in cervical mucus happen very rapidly. Serum contraceptive steroid levels peak approximately 2 hours after oral ingestion [22]. One study demonstrates cervical mucus reaching its maximum unfavorability 3-4 hours after ingestion, and others studies show the arrest of sperm migration to occur within 30 minutes to 2 hours [7,23]. While these older studies are limited in that progestin administration does not coincide with peak estrogen effects on mucus, the demonstration that cervical mucus changes occur faster than other progesterone mediated effects on the reproductive system suggests that possibly direct (non-nuclear) pathways are involved [7]. At least two classes of membrane associated progesterone receptors (MAPRs) have been described; the progesterone membrane component 1 and 2 (PGRMC1, PGRMC2) and the membrane progestin receptors α and β (mPRs) [21]. These receptors have been shown to bind progesterone and carry out functions in other reproductive tract tissues through non-nuclear mechanisms. However, whether progesterone could be involved with the inhibition of an ion channel or block the exocytosis of secretory granules of the cervix is completely unknown[15,24].

Clarifying progesterone’s regulation of mucus would have large implications on our evaluation of cervical mucus as a contraceptive target. While many current methods rely on mucus thickening for contraception, the potency, timing, and mediation of these transformations are poorly understood. Answering these questions will contribute to the improvement of existing hormonal approaches and provide insight into new targets for non-hormonal contraceptive methods.

1.1.2 Objectives and hypothesis

Hypothesis: Contraceptive action of progestogens occur through direct effects on cervical mucus and not indirectly through reduction in systemic estrogen.

Primary Objective: Using ovarian suppressed women, we seek to individually evaluate the effect of E_2 and progestin on cervical mucus to better understand its hormonal regulation. To do this we will:

1. Create and validate an artificial model of the menstrual cycle using exogenous E_2 and P_4 replacement in ovarian suppressed women.
2. Evaluate effects of increasing estrogen levels on cervical mucus.
3. Evaluate the timing of both the onset, duration and termination of progestin actions on cervical mucus following estrogen priming.
4. Compare the effects of estrogen withdrawal to the synthetic progestin norethindrone.

Secondary Objectives:

1. To determine if membrane bound progesterone receptors are present in the cervix and are regulated by E_2 / P_4 .

1.2 Previous Similar Studies

Much of the literature examining effects of progestins on cervical mucus originate from the 1960's and 1970's during the advent and introduction of progestin only contraception. These studies all had similar methods [18,23,25–31]. After baseline measurements were taken, a group of normal cycling women were started on a progestin-only treatment one of the first few days of the following cycle. Laboratory and clinical measures were assessed serially with varying degrees of frequency including serum and urine hormonal levels to assess hormone profiles, basal body temperature, vaginal cytology, endometrial morphology and mucus characterization through qualitative changes (Insler scoring) and sperm-mucus interaction (through either *in vitro* penetration testing or post-coital testing). Findings consistently demonstrated changes in mucus characteristics with ovulation including lower spinnbarkeit scores, poor ferning, increases in viscosity, greater cell content and decreases in volume [18,25,28]. Results with respect to sperm penetration were mixed, as some tests used a post-coital test while others used an *in vitro* sperm penetration. While some studies demonstrated essentially zero penetration at peak progestin levels following administration [23,26,31], others demonstrated decreased penetration, but with some failures [25,28,31,32].

In addition to mucus changes, these studies demonstrate that progestin-only pills had a range of effects including suppression of proliferative activity in the endometrium, suppression of midcycle FSH and LH peaks, and suppression of ovulation in 15-70% of cycles[7,18,20,32]. An important feature of our proposed study involves eliminating the variability due to the timing of natural ovulation through the use of artificial cycles. The progestin intervention occurred at variable times when mucus may not have been at its most favorable. Moreover, since ovulation is not fully inhibited, there are likely endogenous progesterone effects in addition to exogenous progestin effects. No previous studies disentangle this confounding influence on cervical mucus.

The other advantage of our methodology is it allows reappraisal of the time course of progestin effects. Currently, the commonly held belief among providers is that progestin effects have rapid onset and rapid offset. In reality very few studies examine this outcome and even then, in those older studies, rigid study design is not employed. The study by Cox et al. evaluating six users of .5 mg of oral megestrol acetate showed that mucus penetration sharply falls from full penetration to no penetration in 2 hours, followed by an equally steep return to penetrative mucus at 22-24 hours[23]. Cox's study contains almost no measures of statistical significance only pooled data of the 6 subjects is presented. Lebech et al., examining 17 patients, administered .25mg of megestrol acetate orally and noted "normal penetration of sperm" 38 hours later. In addition to no statistics, or measurements of sample variation, Lebech's study also noted anovulatory cycles in some of his controls.

Perhaps more interesting than the literature reported is the absence of literature supporting current guidelines of oral administration. The most definitive review on progestin only oral contraceptives is a 195 page supplementary report published in *Contraception* in 1994 by McCann and Potter[22]. The review details all aspects of pill properties including mode of action, metabolic effects and drug interactions based on over 530 references. From this review, in the final section entitled "Taking POPs effectively" the authors endorse that taking the pill every single day at the same time is essential[33]. In addition to the papers described above, the reference for this recommendation consists of two letters of personal correspondence and a textbook written for general practitioners to become more familiar with basic principles of birth control methods. Yet McCann's guidelines serve both as the reference and the basis for similar recommendations found in Speroff and Darney's *A Clinical Guide for Contraception* and Hatcher's *Contraceptive Technology*[34,35].

Also contained within the progestin only literature, there is some suggestion that the type of progestin and the mode of delivery may affect the rate at which changes in cervical mucus

occur. Several old mini pill studies comparing different progestins, including many of which are either unavailable or no longer widely used, detail that there appear to be varying degrees of mucus response depending on the progestin[26,32]. The results of these studies are difficult to evaluate as they compare specimens in different women. Similarly, the topic of dose-dependent changes on mucus is essentially unexplored. As for route of administration, both Depo-Provera and the Levonorgestrel implant (Norplant) having been shown to cause more gradual declines in mucus quality after administration[36,37]. More recent evaluations of the LNG-IUS system has shown that users of the LNG-IUS have mucus that is substantially different from usual metrics and highly impenetrable by sperm compared to controls[8]. Moreover, temporal studies of LNG-IUS and cervical mucus indicate that mucus quality and sperm penetration is rapidly, but not universally altered following insertion[38].

It has been demonstrated that peak protein levels of one of the most important secreted protein in cervical mucus MUC5b, occurs at least one day after peak expression of mRNA levels[39]. Therefore there is interest in finding a regulating mechanism for “fast” mucus changes. Current research has focused on non-genomic estrogen receptors as well as the role of membrane channels in hydration[24,40–43]. In the case of progesterone, at least two classes of membrane associated progesterone receptors (MAPRs) have been described, including progesterone membrane component 1 and 2 (PGRMC1, PGRMC2) as well as membrane progesterin receptors α and β (mPRs)[21]. Both PGRMC1 and mPRs have been demonstrated to serve functions in the endometrium and oviduct via non-nuclear protein cascades[44][45] (See Figure 1 in addendum). PGRMC1 for example has been shown to impair binding of oxytocin with its membrane receptor and that it mediates an anti-apoptotic effect in ovarian cells via non-nuclear protein cascades[44,46]. Although PGRMC1 expression was noted in Hela cells, which are derivative from a squamous cell cervical cancer line, neither PGRMCs nor mPRs have been identified in human mucus producing endocervical cells[47]. Initial steps towards exploring this possible source of regulation further would be to confirm the presence of non-nuclear progesterone receptors in these cells.

1.3 Design and Methodology

General summary of the approach:

This study will consist of two parts: (1) examining cervical mucus during a normal cycle (2) suppressing endogenous hormone production, adding back therapy through estrogen patches and randomizing women to assess the impact of estrogen withdrawal versus progestin administration on mucus. Serum, cervical mucus and endocervical brush samples will be collected at defined points throughout the experiment. Figures 2 and 3 below illustrate the experimental design.

Figure 2: Sampling Plan for Baseline Cycle

[figure not shown]
[figure not shown]

Figure 3: Sampling and Hormone and Replacement Plan for Randomized Cycles

1.3.1 Subject Selection

A prospective cohort of healthy, normally menstruating women will be recruited. No subpopulations of women will be specifically included or excluded, and no special classes of subjects will be enrolled. For detailed inclusion/exclusion criteria see Table 1.

Table 1: Inclusion and Exclusion Criteria

Inclusion Criteria	Exclusion Criteria

 • Normal menstrual cycles of 25-35 days in length for at least previous 3 cycles • 21-40 years of age • BMI >18, <35 • Serum P₄ ≥ 3 ng/ml on single sample collected between days 18-25 of self-reported menstrual cycle • Flexible schedule allowing blood draws on less than 48 hour notice • In good general health • Commit to using non-hormonal contraceptive methods without spermicide during study period except those prescribed in the experimental protocol • No objections to taking study drugs • No objections to refraining from intercourse the night before any sampling and willing to using condoms during vaginal intercourse. 	
 • Oral contraceptive use or other hormone supplement within the preceding 2 months • Women with current cervical infection • Evidence of abnormal cervical cytology • Use of any IUD for contraception • Long-acting hormonal contraceptive use in the past 12 months (e.g., Depo-Provera®) • Contraindications to study drugs • Current or past pregnancy within the previous 6 months or currently trying to conceive • Desiring to conceive in the next 8 months • Breastfeeding in the past 2 months • Diagnosed Diabetes or Metabolic Syndrome • Diagnosed Polycystic Ovary Syndrome • History of, or self-reported, substance abuse • Smoker • Previous infertility treatment excluding male factor issues • Use of an investigational drug within the past 2 months • History of excisional or ablative treatment procedure on cervix (ie. LEEP, Cryotherapy, Cold Knife Cone) • Current treatment for a vaginal infection such as Bacteria Vaginosis • History of Venous thromboembolism (VTE) or inherited thrombophilias

1.3.2 Treatment Cycles:

The study will begin with the first day of menstruation following enrollment. This cycle will be untreated but monitored and sampled (see figure 2 and section 1.3.3 for sample collection schedule). In order to determine points corresponding to late follicular and ovulation in these women, subjects will be provided with Clearblue® Ovulation Test (Inverness Medical Innovations, Inc., Waltham, Massachusetts). The fertility monitors test for urinary metabolites of LH, which will aid in staging of the menstrual cycle. At the end of the natural cycle treatment (menses), subjects will receive the gonadotropin releasing hormone (GnRH) agonist Lupron® (leuprolide acetate; Abbvie, Chicago, IL) in a 11.25 mg single injection which is sufficient for 3 months of continuous suppression. At 3 weeks, a visit will occur where an additional blood aliquot will be obtained and sent to the endocrine lab to confirm suppression. A phone call following confirmation will be made to instruct the subject to begin patches. We have previous experience with this model that shows ovarian suppression is reliably achieved at 21 days[48]. After confirmation of ovarian suppression and collection of baseline serum samples, all subjects will undergo replacement of endogenous estrogen with patches.

Transdermal E₂ patches changed twice weekly (Vivelle-Dot®, Noven Pharmaceuticals Inc.; Miami, FL) will be used to replace E₂, with a 0.1 mg/day transdermal dose having been previously shown to restore circulating E₂ levels in ovarian-suppressed women to 89 ± 38

pg/ml[49], levels comparable to the late follicular and luteal phases of natural cycles[50,51]. Women will be kept at this level until prior to a randomized intervention at which point the day prior we will bring the women to mid-cycle levels (.3 mg/day). Levels of E₂ in normal women during the mid-cycle surge have been reported to be 335 ± 21 pg/ml [51] or approximately 3 times the E₂ concentrations measured with a 0.1 mg/day transdermal E₂ dose[49]. Pharmacokinetic data of E₂ patches demonstrates that half-life is approximately 5.9-7.7[52]. Again previous use of this replacement schedule demonstrates that these levels approximate serum hormone levels of normally cycling women[48]. In between interventions the subject will be maintained at the .1 mg /day level to prevent menopausal symptoms. At the end the subject will be placed on oral micronized P₄ (200 mg/day) for 5 days to trigger a withdrawal bleed. This dose causes circulating P₄ levels similar to those detected during the luteal phase of the menstrual cycle[56].

Table 3: Sample Collection Schedule for Natural Cycles.

Experimental Cycle	Phase of Cycle	Days of Collection
Natural Menstrual Cycle	Early Follicular	Days 3-5
	Mid Follicular	Days 7-9
	Late Follicular	Days 11-13
	Ovulation	Days 0-1 Post LH-Surge ("Peak" fertility home test result)
	Mid Luteal	Days 6-9 Post LH Surge

For the intervention phase women will be randomized to receive two different interventions twice to assess the effects of a single dose of oral progestin, Norethindrone (NET) versus estrogen withdrawal only. The dose of NET .35 mg is the same dose found in commercially sold oral progestin-only contraceptives[57]. During the intervention cycles, women will be started at the .1 mg dose. After at least 5 days the subject can undergo an intervention. The day prior to the intervention the subject will have her patches increased to the .3mg level. On the day of intervention that subject will either leave the patches on and take a NET pill or the subject will have the patches removed. At this point, in order to evaluate temporality of effect, we will collect several timed samples over 24 hours from initiation of intervention (see Figure 4). Following this 24-hour collection, all patients will be placed again on .1 mg patch for ~5 days as a washout. Recognizing there is some burden to allotting time to come to the visits, the subjects may schedule their next intervention a time beyond 5 days that is convenient for them. Again, we will only increase to the .3 mg the day before the scheduled intervention is to take place. All in all, the subject will receive 4 intervention/24 hours sampling periods, 2 of which will be the NET and 2 of which will be the estrogen withdrawal. See Figure 3 for replacement and collection schedule during this part of the experiment. Finally, after the progesterone withdrawal, subjects will be placed on a low dose oral contraceptive pill (.35 mcg ethinyl estradiol/1 mg norethindrone acetate) for management of side effect related to leuprolide.

Figure 3: Sampling and Hormone and Replacement Plan for Randomized Cycles

[figure not shown]
[figure not shown]

Figure 4: 24hr Sampling Schedule

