Figure 3 shows the sample collection during the second part of experiments when we replace hormone exogenously. The patient will undergo 4 periods of sample collection each spanning a 24 hours period. The subject upon initiation of the randomized intervention (estradiol withdrawal vs. NET). Each collection period will include six samples (see figure 4). This sampling schedule will take place over 2 days. Beginning in the morning, we will collect samples at time 0 (initiation of intervention), 2,4, and 6 hours. They will then return the next morning for collections at 22 and 24 hours. There will also be one sample collection at the beginning of the period (3 weeks after the Lupron shot), to confirm that ovarian suppression has been achieved and mucus is poor.

This means there will be 5 collections in the natural cycle and 4 (interventions) x 6 (collections/intervention) + 1 (prior to start of period) for a total of 30 collections. These will occur over 15 visits. Enrollment can also be combined with the first collection visit to make 14 total visits). Measure outcomes are further described below.

Study Month	-	Month 1					Month 2										
		Screening	Enrollment	Natural Cycle				Lupron Injection	Ovarian Suppression	Randomized Cycles							
EF	MF			LF	Ovulation	ML	24 hr collection			24 hr collection		24 hr collection		24 hr collection			
0	1			2	3	4	5	6		7	8*	9**	10*	11**	12*	13**	14*
Consent	X																
Medical History	X																
Urine Pregnancy Test	X																
Vitals (Blood Pressure, Pulse)	X																
Height and Weight	X																
Serum Progesterone+ Estrogen Levels	X		X	X	X	X	X	X	X*	X**	X*	X**	X*	X**	X*	X**	X**
Cervical Mucus Scoring			X	X	X	X	X		X*	X**	X*	X**	X*	X**	X*	X**	X**
Sperm Penetration Testing@					X	X	X		X*	X**	X*	X**	X*	X**	X*	X**	X**
Endocervical cell collection for RNA testing			X	X	X	X	X		X*	X**	X*	X**	X*	X**	X*	X**	X**
Receive Home Fertility Test Kit		X															
Receive Study Diary		X															
Receive Combined Oral Contraceptive (at end of visit)																	X
Lupron or equivalent Injection							X										
Receive Study Patches																	
Receive Progesterone Pills																	
Receive NET									X#		X#		X#		X#		
Study wrap-up																	
Estimated time	90 m	30 m	15 m	15 m	15 m	15 m	30m	15m	8hr	2.5hr	8hr	8hr	2.5hr	8hr	2.5hr	2.5hr	2.5hr

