* Visits 8, 10, 12, and 14 will include serum hormone levels, cervical mucus scoring, sperm penetration testing at 0,2,4,6 hours. Endocervical sampling will be done at 6 hours.

** Visits 9, 11, 13, and 15 will include serum hormone levels, cervical mucus scoring, sperm penetration testing at 22 and 24 hours (from previous day). Endocervical sampling will be done at 24 hours.

You will be randomized to receive NET at 2 out of the 4 24 hr visits (visits 8, 10, 12, and 14).

@ Sperm Penetration Testing is an experiment done in a laboratory where donor sperm is placed in extracted cervical mucus and evaluated for their ability to swim.

Please note the protocol will have certain flexibility regarding initiation of certain parts of the study in order to minimize study burden on the subjects. Enrollment (visit 2) and the first collection (visit 3) can be combined for one longer visit if the subject desires. During both natural and artificial cycles, a personalized study schedule regarding hormone replacement plan and sampling dates will be given to the patient. A study diary will be kept by the patient recording all medications taken by the patient as well as the daily results of the home fertility test. Almost all sampling visits have a 3-day window during the natural cycle except days marking

ovulation in the natural cycle. Similarly, the time between interventions is flexible as long as they are at least 5 days apart and the subject is able to come for back-to-back days of the 24-hour collections in the replacement cycle. Recognizing that the 24-hour samplings are time consuming and potentially burdensome, this gives flexibility to the subject on when these days occur. Also, as this is well within the three-month suppression period of leuprolide, offering this flexibility should not be a problem.

Moreover, cycles themselves can be initiated with some flexibility. Following leuprolide administration, the artificial cycle can begin between 21 to 28 days later allowing for subsequent visits to occur on weekdays or times best suited for the subject.

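### In the visible text, pregnancy is not re-tested between the untreated natural cycle and the single three-month leuprolide injection (low-severity safety point)

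*Combined protocol and SAP*

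**What the plan says.** - **Eligibility (section 1.3.1, Table 1).** Current pregnancy, pregnancy in the past 6 months, trying to conceive, and wishing to conceive in the next 8 months are all exclusions. Women must use non-hormonal contraception without spermicide and be willing to use condoms. Abstinence is asked only for the night before sampling.
- **Pregnancy test (section 1.3.3, Monitoring and evaluation, visit schedule).** The row "Urine Pregnancy Test" carries one mark, in the same first position as consent and medical history, that is, at screening.
- **Natural cycle (section 1.3.2).** "The study will begin with the first day of menstruation following enrollment", and that cycle is sampled but untreated.
- **Injection (section 1.3.2).** "At the end of the natural cycle treatment (menses), subjects will receive the gonadotropin releasing hormone (GnRH) agonist", as one 11.25 mg dose of leuprolide giving three months of suppression. No test is mentioned at this step.
- **After the injection (sections 1.3.2 and 1.3.8).** Blood is drawn at 3 weeks to confirm suppression. The serum assays listed are LH, FSH, estradiol and progesterone.
- **Schedule entry for the dose (section 1.3.3).** The row "Lupron or equivalent Injection" has one mark. Its position is examined in the working.

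**The concern.** The screening test is done before the natural cycle starts, so it cannot detect a conception in that cycle. The women have confirmed ovulation, are not using hormonal contraception or an IUD, and may have intercourse with condoms. The first study drug is then a depot that acts for three months and cannot be taken back. The protocol's own pregnancy exclusion is therefore not re-checked by a test at the one moment when re-checking could prevent an exposure. The 3-week blood sample might stop a pregnant woman from going on to patches, but only after she has had the dose.

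The stake is participant safety. No estimate, test or comparison in the analysis depends on it. The visible documents do not describe leuprolide's effects in pregnancy, so the point rests only on the protocol's own exclusion.

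**Working it through.** **1. Tests in the visible text.** At screening: 1. Between the start of the natural cycle and the injection: 0. After the injection: 0. The text between sections 1.3.13 and 1.5 was not available, so these counts apply only to what can be read.

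**2. Age of the screening test.** One whole natural cycle lies between screening and an injection given at the next menses. Eligibility asks for 25 to 35 days in at least the previous three cycles. If the study cycle is similar, the test is about 25 days old or more. This is an expectation and not a bound, because the criterion describes past cycles.

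**3. Where the schedule puts the injection.** Numbering the columns from screening as 1:
- The five natural-cycle mucus-scoring marks fall in columns 3 to 7, so the mid-luteal visit is column 7.
- The injection mark is also in column 7.
- The time entry for column 7 is 30 minutes, against 15 for each of the other four natural-cycle visits.
- The text says of the collections "These will occur over 15 visits" and "Enrollment can also be combined with the first collection visit to make 14 total visits". Enrollment 1 + natural cycle 5 + suppression check 1 + intervention days 8 = 15, or 14 with enrollment combined. No visit is left for a separate injection.

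Against this, section 1.3.2 says menses, the schedule header lists the injection under its own label, and the table is damaged: its time row has 17 entries for 16 visits (0 to 15). Visit numbers also disagree. One sentence reads "Enrollment (visit 2) and the first collection (visit 3) can be combined for one longer visit", whereas the count of 15 needs enrollment to be visit 1.

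Timing: Table 3 sets the mid-luteal visit at 6 to 9 days after the LH surge, and section 1.3.3 puts ovulation 24 to 36 hours (1 to 1.5 days) after the surge. That gives 6 − 1.5 = 4.5 to 9 − 1 = 8 days after ovulation, before the menses that section 1.3.2 relies on.

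**4. Size.** Section 1.3.11 plans ten women, of whom 7 finish under the original protocol, so 10 − 7 = 3 remain if ten is the enrollment target. The documents give no pregnancy rate. Two quantities are assumed: p, the chance of conception per woman in the natural cycle, 0.2% to 1.5%; and q, the share of conceptions with bleeding taken for menses, 5% to 25%.

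| Quantity | Formula | Low | High |
|---|---|---|---|
| Expected conceptions | 3p | 0.006 | 0.045 |
| At least one conception | 1 − (1 − p)³ | 1 − 0.998³ = 0.6% | 1 − 0.985³ = 4.4% |
| At least one exposed pregnancy, injection after menses | 1 − (1 − pq)³ | 1 − 0.9999³ = 0.03% | 1 − 0.99625³ = 1.1% |

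If the injection were given at the mid-luteal visit, menses would not act as a check and the 0.6% to 4.4% row would apply.

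**The case against.** The strongest reply is that absence has not been shown. Part of the protocol is missing from the available text and may contain a testing rule. The extracted schedule is also weak evidence of absence. Its rows for patches, progesterone pills and study wrap-up carry no mark at all, and mucus scoring is unmarked at the 3-week visit although the text calls for a collection there. This stands, and it is why the request is conditional.

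The second reply is that the plan does guard against pregnancy. Women wishing to conceive are excluded, contraception is required, the research unit supplies condoms, and section 1.3.2 ties the dose to menses. These measures do lower the risk, so menses is not the only barrier. None of them tests pregnancy status on the day of dosing.

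A reader might infer that the bleed goes unconfirmed, because the diary is described as "recording all medications taken by the patient as well as the daily results of the home fertility test" and menses is not listed. The documents do not support that. The study start and the early sampling days are defined by menses, so staff must obtain those dates somehow.

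A reader might also stress that section 1.3.4 calls the use of leuprolide unapproved. There the word refers to a different patient population, and the section expects no significant added risk. It adds little weight here.

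**Conclusion.** The point holds for the visible text, as a low-severity safety improvement. Pregnancy status is tested at screening and not again before a three-month dose that cannot be withdrawn. On the assumed rates, the chance of at least one exposed pregnancy among about three women is 0.03% to 1.1% if the injection waits for menses. The range depends on p, q and the count of three; none of the rates comes from the documents.

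Two stronger readings are tempting. The first is that the full protocol has no re-test at all, which cannot be concluded while a section is missing. The second is that the schedule shows the injection planned before menses. The column position, the longer visit time and the visit count point that way, but a damaged table cannot override the explicit wording of section 1.3.2. It is a discrepancy to reconcile and not an established error, and the 0.6% to 4.4% figure applies only if that reading proves right. The trial's analysis is not affected.

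**What to change.** First check whether the section missing here already requires a test before the injection. If it does, only the schedule needs to show it. If it does not:

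1. In section 1.3.2, state that leuprolide is given only after menses has begun and after a negative urine pregnancy test on the same day, and that it is not given if menses is absent or the test is positive.
2. In the section 1.3.3 schedule, mark the pregnancy test and the injection together, after the mid-luteal visit. This also settles the discrepancy with section 1.3.2. A test at the mid-luteal visit is no substitute, because menses has not yet occurred.

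The cost is one dipstick per woman for about three women, using a test the trial already performs, and possibly one short visit at menses. If that visit is added, the count becomes 16 (15 with enrollment combined). The 30 collections and the analysis do not change. Aligning the visit numbers and adding the menses start date to the diary would be useful housekeeping but are not essential.
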